- Chronic kidney disease: inpatients with at least once 1 discharged diagnosis CKD (ICD-10 N18), or inpatients with the last estimated glomerular filtration rate (eGFR, calculated by CKD-EPI equation) <60 mL/min/1.73 m^2 or prescription of dialysis, but not with the diagnosis of acute kidney injury (ICD-10 N17); or outpatients with at least 2 diagnosis of CKD (the first diagnosis will be the index diagnosis, and the time interval between diagnoses is not restricted) or with two consecutive eGFR (calculated by CKD-EPI equation) <60 mL/min/1.73 m^2 by 90 days or more.
- High cardiovascular risk: patients with at least 1 discharged diagnosis or 2 outpatient diagnosis of hypertension (the first diagnosis will be the index diagnosis, and the time interval between diagnoses is not restricted) (ICD-10 I10-I15); or at least 1 discharged diagnosis or 2 outpatient diagnosis of hyperlipidemia (ICD-10 E78.001-E78.003, E78.101, E78.203, E78.301-E78.304, E78.306, E78.401, E78.501, E78.902)

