6.3 STUDY POPULATION

Diabetic/non-diabetic patients with/without established cardiovascular disease, chronic kidney disease, or at high cardiovascular risk.

Inclusion Criteria:

- 1) Patients in the Tianjin regional database from 01/01/2015 to 31/12/2019.
- 2) Group A: patients with diagnosis of diabetes, and with diagnosis of cardiovascular disease, heart failure, chronic kidney disease or at high cardiovascular risk;
- 3) Group B: patients with diagnosis of diabetes, but not with diagnosis of cardiovascular disease, heart failure, chronic kidney disease or at high cardiovascular risk;
- 4) Group C: patients with diagnosis of cardiovascular disease, heart failure, chronic kidney disease or at high cardiovascular risk, but not with diagnosis of diabetes;
- 5) Group D: patients without diagnosis of cardiovascular disease, heart failure, chronic kidney disease or at high cardiovascular risk, and without diagnosis of diabetes. We will randomly select a group of non-diabetic patients without any of the above diseases by matching on age and gender.

Definition of diabetes, cardiovascular disease, chronic kidney disease and high cardiovascular risk

- Diabetes: patients with at least 1 discharged diagnosis or 2 outpatient diagnosis of diabetes (ICD-10 E10-E14)
- Cardiovascular disease: patients with at least 1 discharged diagnosis or 2 outpatient diagnosis of ischemic heart diseases (ICD-10 I20~I25); or patients with at least 1 discharged diagnosis or 2 outpatient diagnosis of cerebrovascular diseases (ICD-10 I60~I69); or patients with at least 1 discharged diagnosis or 2 outpatient diagnosis of ischemic peripheral artery disease (ICD-10 E10.501, E11.603, E14.501, E14.606, E14.503, I73.9, I99.03, I99.04);
- Heart failure: patients with at least 1 discharged diagnosis or 2 outpatient diagnosis of heart failure (ICD-10 I50);
- Chronic kidney disease: inpatients with at least once 1 discharged diagnosis CKD (ICD-10 N18), or inpatients with the last estimated glomerular filtration rate (eGFR, calculated by CKD-EPI equation) <60 mL/min/1.73 m² or prescription of dialysis, but not with the diagnosis of acute kidney injury (ICD-10 N17); or outpatients with at least 2 diagnosis of CKD or with two consecutive eGFR (calculated by CKD-EPI equation) <60 mL/min/1.73 m² by 90 days or more.

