- High cardiovascular risk: patients with at least 1 discharged diagnosis or 2 outpatient diagnosis of hypertension (ICD-10 I10~I15); or at least 1 discharged diagnosis or 2 outpatient diagnosis of hyperlipidemia (ICD-10 E78.001-E78.003, E78.101, E78.203, E78.301-E78.304, E78.306, E78.401, E78.501, E78.902)

Exclusion Criteria:

- 1) Patients with non-Chinese nationalities;
- 2) Duplicated storage (records with same inpatient code).

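### Hypertensive renal and heart failure codes inside I10-I15 count as high cardiovascular risk but not as CKD or heart failure, so the CKD rows of SAP Table 1 are understated by an unknown amount

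*SAP*

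**What the plan says.** SAP 6.3 sets out one rule per condition.

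- High cardiovascular risk: "High cardiovascular risk: patients with at least 1 discharged diagnosis or 2 outpatient diagnosis of hypertension (ICD-10 I10~I15", or a hyperlipidaemia diagnosis under the same counting rule. Protocol 9.2.2 has the same range: "ICD-10 I10-I15); or at least 1 discharged diagnosis or 2 outpatient diagnosis of hyperlipidemia". Neither document takes any subcode out of it.
- Heart failure: "Heart failure: patients with at least 1 discharged diagnosis or 2 outpatient diagnosis of heart failure (ICD-10 I50". No other code and no laboratory route is given.
- CKD, inpatient code route: "inpatients with at least once 1 discharged diagnosis CKD (ICD-10 N18".
- CKD, inpatient routes that need no code: "inpatients with the last estimated glomerular filtration rate (eGFR, calculated by CKD-EPI equation" below 60, "or prescription of dialysis, but not with the diagnosis of acute kidney injury (ICD-10 N17".
- CKD, outpatient routes: "or outpatients with at least 2 diagnosis of CKD or with two consecutive eGFR (calculated by CKD-EPI equation" below 60, at least 90 days apart. This clause names no code of its own for the two diagnoses.

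One qualifying condition is enough for group membership: "Group A: patients with diagnosis of diabetes, and with diagnosis of cardiovascular disease, heart failure, chronic kidney disease or at high cardiovascular risk". Group C uses the same list for patients without diabetes.

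SAP Table 1, the primary table, has component rows for cardiovascular disease, CKD and high cardiovascular risk under Groups A and C. It does not say whether a patient may appear in more than one row. None of SAP Tables 1 to 4 has a heart failure row.

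**The concern.** The objectives rest on the contrast between established disease and mere risk. ICD-10, the classification the plan adopts, has combination codes that record hypertension and the organ failure it caused in one entry: I11.0 and I13.0 for heart failure, I12.0 and I13.1 for renal failure, I13.2 for both. All five fall inside I10-I15 and none falls under I50 or N18. Where a hospital uses the combination code alone, the plan's rules record the hypertension and lose the organ disease.

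At stake is the CKD component of the primary table, in diabetic and non-diabetic patients alike, and heart failure wherever it is reported separately. Protocol 9.9 itself accepts that CKD appears under more than one code in the charts, yet the code route names one.

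**Working it through.** There is no figure in the plan to reproduce. The check is to apply the SAP 6.3 rules to example patients and see where each one lands.

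**Inputs.** High risk = I10 to I15. Heart failure = I50. CKD = N18, or a qualifying low eGFR, or (inpatients) dialysis. The N17 exception is read as applying to the inpatient eGFR and dialysis routes. Cardiovascular disease (CVD) = I20 to I25, I60 to I69, or the listed peripheral artery codes. The meaning of I11.0, I12.0 and I13.x comes from the ICD-10 category titles; the documents do not print them.

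| Patient's records | CVD | Heart failure | CKD | High risk | Group A or C |
|---|---|---|---|---|---|
| I11.0 or I13.0 only | no | no | no | yes | yes |
| I12.0 only, no low eGFR, no dialysis | no | no | no | yes | yes |
| I12.0, inpatient, last eGFR below 60 | no | no | yes | yes | yes |
| I12.0, inpatient, dialysis | no | no | yes | yes | yes |
| I12.0, inpatient, last eGFR below 60, and N17 | no | no | no | yes | yes |
| I11.0 and I50 | no | yes | no | yes | yes |
| I11.0 and I25 | yes | no | no | yes | yes |
| I50 only | no | yes | no | no | yes |

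I13.1 and I13.2 behave like I12.0 for CKD, and I13.2 behaves like I11.0 for heart failure.

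**What moves.** Every patient in the table is already in Group A or C. Counting the subcodes as CKD or heart failure as well therefore changes the group totals and the composite primary proportions by 0. Only the component split can move. The CKD row is short by exactly the patients with I12.0, I13.1 or I13.2 and no other CKD route.

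**Scale.** The documents give no frequency for these codes. For illustration only, let s be the share of patients carrying a renal subcode and m the share of those with no other CKD route. The shortfall in percentage points is 100 × s × m.

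- s = 0.005, m = 0.10: 100 × 0.0005 = 0.05 points, or 50 per 100,000 patients.
- s = 0.02, m = 0.50: 100 × 0.01 = 1.0 point, or 1,000 per 100,000.
- s = 0.05, m = 0.90: 100 × 0.045 = 4.5 points, or 4,500 per 100,000.

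Both inputs are assumptions. The range shows only that the effect could be negligible or material.

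**The plan's own precedent.** E10.501, E11.603, E14.501, E14.503 and E14.606 lie inside the diabetes range E10-E14 and are also listed as peripheral artery disease. One code already serves both the underlying disease and the organ disease. The hypertension range gets no such treatment.

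**The case against.** The strongest reply is that the code list is not the only way in. Nothing makes the categories exclusive. A patient with I12.0 who also has N18, a qualifying eGFR or a dialysis prescription is counted as CKD, and one with I11.0 and I50 as heart failure. Renal failure is a condition that eGFR and dialysis records would be expected to pick up. This stands, and it limits the point to patients with no such record. It does not remove it: outpatients need two low values at least 90 days apart, N17 blocks the inpatient eGFR and dialysis routes, and heart failure has no non-code route.

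A second reply is that the subcode meanings are not in the documents and that the plan uses locally extended codes, so the local subdivision of I11-I13 cannot be checked here. That is fair. The titles belong to the adopted classification, but the sponsor should confirm them in its own dictionary.

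A third is that the 200-chart review before analysis tests the codes. Protocol 9.7.1 includes CKD in that review; SAP 11 names only cardiovascular disease and high risk; neither names heart failure. The review may reveal the gap, but no rule says what would follow, and the protocol's checklist answers no on analytic control of outcome misclassification (item 10.6).

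A reader might also infer a specific shortfall. For example, an assumed 10-30% of renal-failure patients coded only this way, times the 500,000 of 600,000 diabetic patients without comprehensive information (0.833), gives 0.083 to 0.25, or about 8-25% of the CKD row. The documents do not support that. The 10-30% has no source. It is a share of renal-failure patients, while the CKD row also holds everyone found by low eGFR. Lacking comprehensive information does not mean lacking creatinine, and dialysis is a further route. SAP 8 gives 10,000 where the protocol gives 100,000.

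**Conclusion.** The point holds for the component split. Under the rules as written, a patient identified only by a hypertensive renal or heart failure code, with no I50, N18, qualifying eGFR or dialysis record, is counted as at high risk and not as having CKD or heart failure. The CKD rows of SAP Table 1 are understated by the number of such renal patients, which cannot be estimated from the documents. This rests on the ICD-10 titles applying to the local coding and on at least some hospitals using the combination codes alone.

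Three wider readings should be avoided. Patients with hypertensive organ failure are not in general shown as risk only, because many may qualify by another route. The headline proportions are not biased, because Group A and C totals and the composite primary outcomes do not move. And the heart failure gap changes nothing in Tables 1 to 4, where even I50 patients have no row; it matters only where heart failure is reported separately. Nor do the documents show that hypertensive patients make up most of Groups A and C.

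**What to change.** Before extraction, amend Protocol 9.2.2 and SAP 6.3, keeping the existing counting rule of one discharge or two outpatient diagnoses:

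- count I12.0, I13.1 and I13.2 also as CKD;
- count I11.0, I13.0 and I13.2 also as heart failure;
- keep all of them in I10-I15, so the hypertension count does not change;
- check the subcodes against the local code dictionary;
- state whether the N17 exception applies to the added renal codes;
- state that Table 1 rows may overlap.

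The cost is six code entries in each document and a short statement on N17 and overlap. The records are already pulled under I10-I15, so no new data are needed.

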6.4 STUDY VISITS

Not applicable, this study is based on routinely collected database.

7. VARIABLES

7.1 Exposures

Not applicable. Four groups will be defined according to the diagnosis and laboratory measurements. Diagnosis of diabetes and high-cardiovascular risk differ among groups.

7.2 Outcomes

Our primary outcomes will be the proportion of diabetic/non-diabetic patients with disease/risk. Secondary outcomes include demographic characteristics (e.g. age, gender, insurance payment) and clinical characteristics (e.g. HbA1c, random blood glucose, serum creatine) of patients. Further outcomes include economic burden of disease of diabetic/non-diabetic patients with or without disease/risk (e.g. length of stay, hospital cost).

7.2.1 Primary outcomes

- 1) The proportion of diabetic/non-diabetic patients with established cardiovascular disease, chronic kidney disease, or at high cardiovascular risk.
- 2) The proportion of diabetic patients with established cardiovascular disease, chronic kidney disease, or at high cardiovascular risk among all patients with diabetes;
- 3) The proportion of non-diabetic patients with established cardiovascular disease, chronic kidney disease, or at high cardiovascular risk among patients without diabetes;

Table 1. The proportion of patients with disease or risk among diabetic or non-diabetic patients

| | 2015 | | 2016 | | ... | | 2019 | | Overall | |
|--|-----------------|----------------|-----------------|----------------|-----------------|----------------|-----------------|----------------|-----------------|----------------|
| | Outpatie nts | Inpatient s | Outpatie nts | Inpatie nts | Outpatie nts | Inpatient s | Outpatie nts | Inpatient s | Outpatie nts | Inpatient s |
| | n (%) | n (%) |
| Patients diagnosed with diabetes | | | | | | | | | | |
| Group A (n, %) | | | | | | | | | | |
| with cardiovascular disease | | | | | | | | | | |
| with chronic kidney disease | | | | | | | | | | |
| at high cardiovascular risk | | | | | | | | | | |
| Patients diagnosed without diabetes | | | | | | | | | | |
| Group C (n, %) | | | | | | | | | | |
| with cardiovascular disease | | | | | | | | | | |
| with chronic kidney disease | | | | | | | | | | |
| at high cardiovascular risk | | | | | | | | | | |

Note: Group A: Diabetes with cardiovascular disease, chronic kidney disease or at high cardiovascular risk; Group B: Diabetes without cardiovascular disease, chronic kidney disease or at high cardiovascular risk; Group C: Non-diabetes with cardiovascular disease, chronic kidney disease or at high cardiovascular risk; Group D: Non-diabetes without cardiovascular disease, chronic kidney disease or at high cardiovascular risk;

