## **8. RESEARCH QUESTION AND OBJECTIVES**

The study aims to investigate the clinical characteristics, treatment, and economic burden of disease of Chinese diabetic/non-diabetic patients with/without established cardiovascular disease, chronic kidney disease, or at high cardiovascular risk, including:

[figure not shown]
- Primary objectives: describe the proportion of Chinese diabetic/non-diabetic patients with established cardiovascular disease, CKD, or at high cardiovascular risk including hypertension and hyperlipidemia.
- Secondary objectives: describe the demographic characteristics of the last visit for all patients, and the demographic characteristics of inpatients over time; investigate the clinical characteristic for all patients.
- Further objectives: examine economic burden of disease of Chinese diabetic/non-diabetic patients with/without established cardiovascular disease, CKD, or at high cardiovascular risk; explore the trends of clinical characteristics, treatment patterns, economic burden of inpatients over time.

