## **9.4 DATA SOURCES**

Tianjin regional database cover individual-level health information. There were 40 tertiary hospitals, 32 secondary hospitals and 276 community hospitals Tianjin. It has approximately 200,000 discharges annually. Through integrating EMR systems of hospitals by patient unique identify code, the database contains comprehensive information regarding clinical care, such as patients' basic information, medical advice, diagnosis, laboratory examination, medical records and medical costs. It could be a valuable big data resource for clinical studies. Till 2020, data from 40 tertiary hospitals has been collected, and there were approximately 600,000 patients diagnosed with diabetes in these 40 tertiary hospitals from 01/01/2015 to 31/12/2019. Of these, 100,000 patients were with comprehensive information through integrating EMR systems.

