### **9.9 LIMITATIONS OF THE RESEARCH METHODS**

There is no unique ICD code for cardiovascular disease, CKD or at high cardiovascular risk. Each of those diseases has more than one ICD code in the medical charts. The subjects came from different hospitals; the understanding of ICD code may be different according to different hospitals.

The study is limited in representativeness and generalizability. Of 600,000 patients, only 100,000 patients contained comprehensive information about patients' basic information, medical advice, diagnosis, laboratory examination, medical records and medical costs.

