7.2.2 Secondary outcomes

- 1) The demographic characteristics of the latest visit for all patients, as well as the trends for inpatients over time (2015, 2017, and 2019 respectively). Clinical characteristics of outpatients and hospitalized patients will be described respectively.

Table 2. The demographic and clinical characteristics of the latest visit

| Outpatients | | | | Inpatients | | | | Total patients |
|--|----------------|----------------|----------------|-------------------|----------------|----------------|----------------|-----------------------|
| Group A | Group B | Group C | Group D | Group A | Group B | Group C | Group D | |
| Demographic characteristics in 2015 | | | | | | | | |
| Age (mean, sd) | | | | | | | | |
| Gender (n, %) | | | | | | | | |
| Insurance payment (n, %) | | | | | | | | |
| Demographic characteristics in 2017 | | | | | | | | |
| Age (mean, sd) | | | | | | | | |
| Gender (n, %) | | | | | | | | |
| Insurance payment (n, %) | | | | | | | | |
| Demographic characteristics in 2019 | | | | | | | | |
| Age (mean, sd) | | | | | | | | |
| Gender (n, %) | | | | | | | | |
| Insurance payment (n, %) | | | | | | | | |

Note Group A Diabetes with cardiovascular disease, chronic kidney disease or at high cardiovascular risk; Group B Diabetes without cardiovascular disease, chronic kidney disease or at high cardiovascular risk; Group C Non-diabetes with cardiovascular disease, chronic kidney disease or at high cardiovascular risk; Group D Non-diabetes without cardiovascular disease, chronic kidney disease or at high cardiovascular risk;

2) The clinical characteristics of the studied population of the latest visit for all patients, as well as the trends for inpatients over time (2015, 2017, and 2019 respectively). Clinical characteristics of outpatients and hospitalized patients will be described respectively.

Table 3. The clinical characteristics of the latest visit

| Outpatients | | | | Inpatients | | | | Total patients |
|---|----------------|----------------|----------------|-------------------|----------------|----------------|----------------|-----------------------|
| Group A | Group B | Group C | Group D | Group A | Group B | Group C | Group D | |
| Clinical characteristics in 2015 | | | | | | | | |
| Department of discharge | | | | | | | | |
| Death | | | | | | | | |
| Clinical characteristics in 2017 | | | | | | | | |
| Department of discharge | | | | | | | | |
| Death | | | | | | | | |

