7.3 Covariates

No applicable. This is a cross-sectional study aiming to describe the proportion, clinical characteristics and economic burden.

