10. DATA ANALYSIS

10.1 Main analysis

The analyses will mainly describe the patient demographic characteristics, comorbidities, complications, treatment pattern and economic burden based on 40 hospitals EMRs of Tianjin regional database.

Characteristics presented as continuous data will be summarized through means, standard deviations, medians, minimum and maximum values; whereas, categorical data will be summarized as counts and proportions.

All tests of statistical significance among different subgroups (age, gender, department, underlying diseases, etc.) will be two-sided unless otherwise specified; any test resulting in $p < 0.05$ will be considered statistically significant. Student-t test, analysis of variance, chi-square test and other rank test will be mainly applied for this study.

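### Yearly disease proportions and inpatient trends are planned as crude figures only, so a change in age-sex mix, or in contributing hospitals if coverage varied, can be mistaken for a real change.

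*SAP*

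**What the plan says.** SAP 7.2.1 sets out the primary table, "Table 1. The proportion of patients with disease or risk among diabetic or non-diabetic patients". It has columns for each year and for the whole period, split into outpatients and inpatients, and rows for Groups A and C and their component diseases. It has no age, sex or hospital breakdown and no standardised column.

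SAP 7.2.2 describes characteristics at the latest visit, "as well as the trends for inpatients over time (2015, 2017, and 2019 respectively"). Table 2 covers age, gender and insurance; Table 3, discharge department and death; Table 4, HbA1c, random glucose and serum creatinine. Among its further objectives, Protocol section 8 plans to "explore the trends of clinical characteristics, treatment patterns, economic burden of inpatients over time".

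SAP 10.1 gives the summary method: "categorical data will be summarized as counts and proportions". SAP 7.3, on covariates, reads: "No applicable. This is a cross-sectional study aiming to describe the proportion, clinical characteristics and economic burden". The checklist in Protocol Annex 2 answers No to stratified analyses (item 10.4) and to analytic control of confounding (item 10.5).

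On hospitals, Protocol 9.4 says: "Till 2020, data from 40 tertiary hospitals has been collected". It gives no start date or yearly completeness for any hospital. Protocol 9.9 concedes that "the understanding of ICD code may be different according to different hospitals".

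**The concern.** A crude yearly proportion is a weighted average over the kinds of patient who attended that year. Cardiovascular disease, kidney disease and hypertension become more common with age. If attenders grow older, the crude figure rises even when the proportion within every age band is unchanged.

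Hospital mix can act in the same way. Group membership rests largely on ICD codes, and the protocol accepts that hospitals may apply them differently. If the set of contributing hospitals changed during the period, the measured proportion could move with no change in any patient's health.

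At stake is how the year columns are interpreted. The plan wants to describe change over time in inpatients, and it sets out the primary proportions by year. As visible, it offers no way to separate a real change from a changed mix, and its limitations section does not warn of the problem.

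**Working it through.** The documents give no yearly figure, age distribution or hospital-specific proportion, so there is no figure of the plan's own to reproduce. Every proportion and mix below is an assumption, chosen to show a range.

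**Formula.** Crude proportion in a year = sum over strata of (share of patients × proportion with disease). The stratum proportions are held fixed between two years, so the true change is zero.

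**Age mix, first illustration.** Assumed proportions are 15%, 45% and 75% for under 45, 45-64, and 65 and over.
- Mix 12/48/40: 0.12×0.15 + 0.48×0.45 + 0.40×0.75 = 0.534.
- Mix 10/43/47: 0.10×0.15 + 0.43×0.45 + 0.47×0.75 = 0.561.
- Spurious change: +2.7 points.

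**Age mix, range.** The assumed starting mix is 25/40/35 for under 50, 50-64, and 65 and over. Patients move into the oldest band, half from each of the other two.
- Steeper gradient (45/70/88%): start 0.25×0.45 + 0.40×0.70 + 0.35×0.88 = 0.7005. Moving 2, 5 or 10 points gives 0.7066, 0.7157 or 0.7310, which is +0.6, +1.5 or +3.05 points.
- Flatter gradient (60/70/80%): start 0.7100. The same moves give 0.7130, 0.7175 or 0.7250, which is +0.3, +0.75 or +1.5 points.

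**Hospital mix.**
- Hospitals with 85% against 68% disease, the former's share rising from 20%: start 0.20×0.85 + 0.80×0.68 = 0.714. A share of 25, 30 or 40% gives 0.7225, 0.731 or 0.748, which is +0.85, +1.7 or +3.4 points.
- Early hospitals at 55%, with entrants at proportion q supplying a share w of later patients: 0.55×(1−w) + q×w. With q = 0.60 and w = 0.25 this is 0.5625 (+1.25 points). With q = 0.70 and w = 0.50 it is 0.625 (+7.5 points). The last case needs entrants to supply half of later patients and to have 15 points more disease.

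**What the remedy does to these examples.** Standardising to one fixed age mix replaces the yearly shares by constants, so the change in the age examples is 0. Restricting to hospitals present throughout gives 0 in the hospital examples where the shift comes from hospitals entering. It would not remove a shift in patient shares among hospitals that were present all along.

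**Would such a shift look significant?** SAP 10.1 sets two-sided p < 0.05 for subgroup tests but does not name year as a comparison, so this applies only if years are tested. Take the 1.5-point shift under the steeper gradient and treat the two years as independent samples. With 20,000 diabetic patients per year (100,000/5, from Protocol 9.4), p < 0.05 would be reached about 92% of the time. With 2,000 per year (10,000/5, from SAP section 8), it would be about 18%. The even split over years is an assumption. The two documents disagree on the number with comprehensive records, and this must be reconciled separately.

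**The case against.** Four points can fairly be made for the plan.

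- **Crude figures are a proper target.** The SAP says "This is a cross-sectional study aiming to describe the proportion, clinical characteristics and economic burden". The observed burden in attenders is a legitimate result. This stands: crude figures should stay, and a reader who inferred that they are wrong would go too far. The gap arises only when years are compared.
- **The primary objective is not a trend objective.** A reader might infer from the year columns that change in the Table 1 proportions is a declared aim. Protocol section 8 and SAP section 5 ask only for the proportion to be described; trends are attached to inpatient characteristics, treatment and cost. This stands. Table 1 invites a comparison of years without promising one, whereas Tables 3 and 4 do serve a stated trend aim.
- **Nothing shows that hospitals joined midway.** The Protocol abstract describes the 2015-2019 source as records from 40 tertiary hospitals, and 9.4 counts about 600,000 diabetic patients in those hospitals over the same period. A reader might infer staggered entry from the words about 2020, but the documents neither state nor exclude it. The same goes for age mix: no shift is shown. Both are risks, not findings.
- **Some protection exists.** SAP Table 2 reports age and gender in the three trend years, so an age shift would be seen there, and outpatients are kept apart from inpatients. This stands in part: a shift that is seen is still not removed, and 2016 and 2018 are not covered.

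Some text may also be withheld. The visible SAP passes from 10.1 to 10.3, and no further-outcome tables can be seen. No conclusion is therefore drawn about the treatment and cost trends. For the visible tables, the No answers to checklist items 10.4 and 10.5 are enough.

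**Conclusion.** The point holds as a cheap improvement. As visible, the plan reports yearly disease proportions and inpatient death and laboratory trends without any means of separating real change from a changed age-sex or hospital mix. The outcome is that a shift can be misread, not that it will be.

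Under the assumed inputs, the spurious movement in a disease proportion is about 0.3 to 3 points for age mix and about 1 to 7.5 points for hospital mix, with the upper hospital figure an extreme case. The documents support no particular value in these ranges. No size was worked out for death or laboratory values, where the reasoning is the same but the inputs are lacking. The hospital part depends on whether coverage varied by year, which the sponsor can settle from the data.

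**What to change.** 1. Keep the crude figures as the description of observed burden.
2. Beside them, give values directly standardised by age group and sex to one fixed distribution, namely all study diabetic patients 2015-2019, for diabetic and non-diabetic patients alike. Do this for the SAP Table 1 proportions and for the death and laboratory rows of Tables 3 and 4. Leave out the age and gender rows of Table 2, where age and sex are themselves the outcome.
3. Report how many hospitals and patients contribute in each year. If coverage varied, repeat the yearly comparison in hospitals with data in every year shown, as a sensitivity analysis.
4. Base any statement that disease or clinical characteristics changed over time on the standardised figures, checked against that fixed panel.

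Birthday, sex and medical organisation are already in the variable list of Protocol 9.3, so no new data are needed. The cost is a few extra columns and some programming. Late-joining hospitals, if there are any, drop out of the one sensitivity analysis only.
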